#### Clarifications:

Only laboratory and haematological abnormalities reported as AEs by investigators (cf. Section 6.8.1 of the protocol for further details) will be analyzed as AEs.

Additional secondary safety endpoints are defined in this SAP (cf. sections 6.3.1, 6.3.2 and 6.3.4).

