(e.g. cosmetic surgery) or in the context of usual management of the disease (including treatment adjustment) will not be considered as an SAE. Similarly, hospitalisation of patients initially treated on an out-patient basis will not be considered as an SAE solely based on the criterion of hospitalisation because, in accordance with Section 6.5, they are to remain in hospital, as are patients initially hospitalised, up to Day 13 or 18. The other seriousness criteria remain valid. This includes hospitalisation for reasons related to non-compliance with treatment, including for a non-serious AE based on the other seriousness criteria;

- results in persistent or significant disability or incapacity;
 - i.e. an AE that leads to significant impairment of the patient's ability to carry out normal activities;
- is a congenital anomaly or birth defect in the child or foetus of a female patient exposed to treatment prior to conception or during pregnancy;
- is an important medical event, i.e. an event that may not be immediately lifethreatening or result in death, but that jeopardises the patient's safety or requires an intervention to prevent one of the outcomes above.

In the study, ALT or AST levels above 3 ULN associated with total bilirubin above 2 ULN will be considered to be SAEs.

Any suspected transmission of an infectious agent via the IMP will also be considered as an SAE.

Any other event defined as serious in the protocol will be reported as an AE and as an SAE in accordance with the procedure described in Section 6.8.5.

For the purposes of the study, hospitalisation for non-complicated delivery will not be considered as an SAE.

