6.8.5. Reporting Requirement for AEs

Information on AEs must be assessed by a physician. The Investigator must determine whether the AE is considered to be serious or not, if necessary with the assistance of the Coordinating Investigator and the study monitor. This classification will determine the reporting procedure for the event.

All SAEs must be reported to the study monitor **immediately, and at the latest 24 hours** after the Investigator becomes aware of the event. The information must be reported, initially, by telephone and/or Short Messaging Service (SMS), and then using the SAE reporting form, which is to be sent by e-mail. The report must

Confidential Page 42 of 83

include the nature of the SAE (if possible a clinical diagnosis), the date and nature of onset, duration, severity, relationship to IMP (assessed with the assistance of the Coordinating Investigator, as needed; reasonable possibility see Section 6.8.7.), measures taken and outcome, as well as any other relevant clinical or laboratory data.

Additional information must be sent as soon as it becomes available, using the SAE follow-up reporting form. All follow-up reports must be sent as quickly as possible and, if possible, within 5 working days after the new information becomes available. A close-out follow-up report must be sent after the final assessment of the case, specifying the outcome of the SAE as "recovery", "recovery with sequelae", "death" etc.

SAEs must be reported using the AE reporting form in the CRF and the SAE reporting form. It should be noted that the SAE reporting form is not the same as the form in the AE section of the CRF. The two forms must be completed in a consistent manner, using the same medical terminology.

All AEs must be recorded in the CRF.

For the purposes of this study, the Coordinating Investigator will be responsible for reporting suspected unexpected serious adverse reactions (SUSARs), considered to be related to the IMP (reasonable possibility), as well as all SAEs, to the Ethics Committee of the country and to other appropriate governing bodies in accordance with national regulatory requirements.

The Sponsor will be responsible for reporting SUSARs and SAEs to the regulatory authorities in accordance with current regulations. The Investigator Brochure will be used as the reference safety information on the IMP, and the expectedness of Aes will be assessed by the Sponsor using this information.

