9.6. Secondary Analyses

9.6.1. Secondary Analysis - Safety

The secondary safety analyses will be performed on the mITT population, i.e. all patients who took at least one tablet of fexinidazole.

The proportion of patients who experienced an SAE and/or an AE leading to treatment discontinuation will be described by system-organ class using Medical Dictionary for Regulatory Affairs (MedDRA) terms and/or NCI CTCAE, version 4.03 (14) and, for certain laboratory parameters, modified CTCAE will be used (see Appendix 6 – CTCAE v4.03 adapted, p 81).

The proportion of patients who experienced at least one AE will be described. Events described using the same term and that occur several times in the same patient will be counted only once. If a patient experiences several events described with the same term, the event with the maximal severity will be included in the analysis. In addition, each SAE will be described in a narrative presenting all aspects of the medical event and the causality assessment.

The incidence of AEs and of SAEs and their respective 95% confidence intervals will be presented by category and by frequency. In other cases, only descriptive statistics will be presented.

Laboratory safety parameters, i.e. haematology and biochemistry, will also be described individually, indicating the proportions of patients by category corresponding to the size of the increase in relation to the ULN for liver function tests (< 1 ULN, 1–2 ULN, 2–3 ULN etc.). Scatter graphs with baseline values on the x-axis and post-treatment values on the y-axis with the bisector indicating the absence of change will be presented. Changes in blood levels over time will be presented in graphs. Shift tables will be provided to supplement signal detection. A listing of patients with clinically significant increases in laboratory parameters will be provided.

Confidential Page 50 of 83

Abnormalities, if any, on ECG tracings recorded on Day 11 will be described.

The proportion of patients hospitalised for a safety problem, including overdose, will also be presented.

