### 6.3. Safety endpoints

As defined in the protocol (Section 2.2.2), the secondary endpoints for the assessment of the safety of fexinidazole will be:

- Occurrence of grade  $\geq 3$  adverse events (AEs), including laboratory and haematological abnormalities (if considered clinically significant), between the first intake of fexinidazole and the end of the observation period\* or the follow-up period (18 months) for non-serious AEs assessed as related to fexinidazole.
- Occurrence of any serious adverse event (SAE) between the first intake of fexinidazole and the end of the follow-up period (18 months).
- Number of patients who prematurely discontinued treatment (i.e. prior to Day 10) or were hospitalised for reasons related to safety\*\* (e.g. including overdose).

\* The observation period extends from the first intake of fexinidazole on Day 1 until the end-of hospitalisation visit (between Day 13 and Day 18) for patients treated in hospital. For outpatients, the observation period extends to the end-of-treatment visit on Day 11.

\*\* A patient will be considered as “hospitalised for reasons related to safety” if he/she experienced a SAE during the treatment period and he/she was initially planned to be treated as an outpatient and he/she was hospitalized during the treatment period.

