### 6.3.2. Laboratory examination

All laboratory parameters recorded in the CRF in sections “Hematology”, “Biochemistry” and “Urinalysis” will be used. For continuous data, the absolute change from baseline to each timepoints will be derived. In addition, continuous laboratory values will be compared to their reference ranges and classified as “<LLN”, “Normal” and “>ULN” at baseline and each timepoints.

For the following parameters, CTCAE grades will be derived as defined in Appendix 6 of the protocol:

- Hemoglobin
- Platelets
- Leukocytes
- Sodium
- Potassium
- Calcium
- Bicarbonates
- Chloride
- Glucose
- BUN
- Creatinine
- Alkaline phosphatase
- ALAT
- ASAT
- Total bilirubin
- Albumin
- Total protein

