#### **8.8.3. Laboratory examination**

For continuous data, a descriptive analysis will be provided for baseline, at each time point and for the changes from baseline at each time point, by cohorts, subgroups and overall.

Changes in blood levels over time will be presented in graphs.

Shift tables between baseline severity (normal value, abnormal not clinically significant, abnormal clinically significant) and severity at each timepoint (i.e. D5, D11, M3, M6, M12, M18) for each laboratory parameters will be provided by cohorts, subgroups and overall.

Scattergrams between baseline value and value at each timepoint (i.e. D5, D11, M3, M6, M12, M18), for each laboratory parameters will be provided by cohorts, subgroups and overall.

Proportions of patients by category corresponding to the size of the increase in relation to the ULN for liver function tests (i.e. ALT, AST, total bilirubin and alkaline phosphatase) will be described (< 1 ULN, 1–2 ULN, 2–3 ULN etc.) by cohorts, subgroups and overall.

A listing of patients with clinically significant abnormalities in laboratory parameters will be provided (cf. [Section 9.1](#)).

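### The SAP never derives the protocol's joint liver SAE criterion (ALT or AST >3 ULN with bilirubin >2 ULN) and has no step to cross-check site reporting of it

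*SAP*

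**What the plan says.** Protocol 6.8.1, in defining a serious adverse event, states: "In the study, ALT or AST levels above 3 ULN associated with total bilirubin above 2 ULN will be considered to be SAEs". No investigator judgement of clinical significance is attached. The same section adds: "Any other event defined as serious in the protocol will be reported as an AE and as an SAE". Protocol 6.8.5 places the decision on seriousness with the site: "The Investigator must determine whether the AE is considered to be serious or not".

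The clarification under SAP 6.3 limits laboratory findings counted as AEs: "Only laboratory and haematological abnormalities reported as AEs by investigators" are analysed in that way. The sentence refers the reader to protocol 6.8.1 for details.

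For the laboratory data themselves, SAP 6.3.2 derives change from baseline and reference-range class, and then: "For the following parameters, CTCAE grades will be derived as defined in Appendix 6 of the protocol". SAP 8.8.3 plans shift tables and scattergrams for each parameter and, for ALT, AST, total bilirubin and alkaline phosphatase, "Proportions of patients by category corresponding to the size of the increase in relation to the ULN for liver function tests". This follows protocol 9.6.1: "Laboratory safety parameters, i.e. haematology and biochemistry, will also be described individually". The output list in SAP 9.1 contains no item that combines a transaminase with bilirubin.

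**The concern.** The SAE criterion is a rule on two or three numbers that are already in the database. Its appearance in the SAE results nevertheless depends on someone at the site noticing that both limits were passed and reporting it. If that does not happen, the AE and SAE tables omit the case. The liver tables cannot show it either, because they give separate counts for each test. Two patients with one raised test each and one patient with both raised can contribute identically to those tables.

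Occurrence of any SAE up to 18 months is a stated secondary safety endpoint. Protocol 1.6 singles out hepatic function as a focus of the additional laboratory data. Protocol 1.4 reports liver-related adverse reactions in an earlier fexinidazole study in Chagas disease. Protocol 8.2 uses the same joint criterion as a reason to stop treatment. A reader of the final report would expect a count of patients who met it, and the SAP as written produces none.

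**Working it through.** **Inputs.** From protocol Appendix 6: ULN of 61 U/L for ALT, 60 U/L for AST and 2.2 mg/dL for total bilirubin. From protocol 6.8.1: the limits 3 ULN and 2 ULN. From protocol 9.1: planned N = 174.

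**Step 1: reproduce the Appendix 6 grade 2 bands.**
- ALT: 3 × 61 = 183 and 5 × 61 = 305, matching the stated band.
- AST: 3 × 60 = 180 and 5 × 60 = 300, matching.
- Bilirubin: 1.5 × 2.2 = 3.3 and 3 × 2.2 = 6.6, matching.

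**Step 2: put the SAE rule on the same scale.** The rule becomes (ALT >183 or AST >180 U/L) and bilirubin >2 × 2.2 = 4.4 mg/dL. The value 4.4 lies inside the grade 2 band of 3.3 to 6.6, so the CTCAE shift tables do not isolate it.

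**Step 3: does the grade ≥3 endpoint capture joint cases?** Not necessarily:

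| ALT (U/L) | Bilirubin (mg/dL) | Meets SAE rule | ALT grade | Bilirubin grade |
|---|---|---|---|---|
| 184 | 4.5 | yes | 2 | 2 |
| 200 | 5.0 | yes | 2 | 2 |
| 305 | 6.6 | yes | 2 | 2 |
| 306 | 4.5 | yes | 3 | 2 |
| 200 | 6.7 | yes | 2 | 3 |

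In the first three rows neither test reaches grade 3.

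**Step 4: can the ULN-multiple tables recover the joint count?** If *a* patients exceed 3 ULN for ALT and *b* exceed 2 ULN for bilirubin, the number with both lies between max(0, *a* + *b* − 174) and min(*a*, *b*). With assumed counts:
- *a* = 5, *b* = 3: between 0 and 3.
- *a* = 8, *b* = 6: between 0 and 6.

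The tables settle the matter only when one of the separate counts is zero. Because the rule says ALT or AST, the number with either transaminase raised is not fixed by the separate ALT and AST tables either.

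**Step 5: what one case would do (illustration only).** Exact 95% limits:
- 0/174: upper limit 1 − 0.025^(1/174) = 2.1%.
- 1/174 = 0.57%: interval 0.01% to 3.16%.

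**Step 6: where could an unreported case still be found?** SAP 9.1 (listings 5 and 5.9) provides individual biochemistry for all included patients in chronological order, and a listing of clinically significant abnormalities. The second listing rests on a judgement that the SAE rule does not require. The first contains the needed values, but someone must read them across tests. Routine post-baseline biochemistry is at Day 11, Month 3 and Month 6, so with full attendance there are about 3 × 174 = 522 panels.

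**The case against.** The strongest answer is that the safeguard lies in reporting. The SAP clarification cites protocol 6.8.1, the section that contains the joint rule. That section obliges sites to report protocol-defined serious events, and protocol 6.8.5 requires SAEs to be reported within 24 hours. Monitors compare source documents with CRFs and SAE forms, centralised monitoring looks for inconsistencies (protocol 11.5), data queries run throughout (11.7), and the DSMB reviews safety data. Sites also have the same combination as a treatment-stopping criterion. SAP 8.8.3 does what protocol 9.6.1 asks, and neither document demands a joint table.

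Most of this stands. A reader might infer that the SAP sets aside the protocol's SAE definition, that such cases will be missed, or that they are invisible in the laboratory outputs. The documents support none of these. The SAP points to the definition, a case is missed only if a site fails to recognise or report it, and the listings hold the values. Nor do the documents show that reconciliation is absent from the trial: the monitoring plan and the data review plan are separate and are not among the documents reviewed. They show only that it is absent from the SAP.

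What the objection does not remove is that none of the safeguards described names this check, that protocol 11.3 rules out 100% source verification, and that even with perfect reporting the SAP gives no summary of joint elevations from the laboratory data.

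**Conclusion.** The point holds as a gap in the SAP: there is no derivation of the joint criterion, no table, figure or count that shows it, and no step that checks reported SAEs against the laboratory values. It is not a loss of data and does not touch the primary endpoint.

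The size cannot be stated, because the documents contain no patient data and give no rate of under-reporting. The comparison of 0/174 with 1/174 shows only that a rare-event result can turn on one patient; it assumes that no other SAE was reported. The grade 2 argument assumes that the Appendix 6 limits are those applied. The case for acting rests on the low cost, the importance the protocol itself gives to hepatic safety, and the fact that the separate tables cannot in general give the joint count.

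A reader might also infer that derived cases should be added straight to the SAE total. The documents do not support that. Protocol 6.8.1 ties an AE to something that occurs or worsens after the IMP is started, 6.8.5 requires assessment by a physician, and 6.8.7 requires a causality assessment. A numerical flag supplies none of these.

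**What to change.** In SAP 6.3.2 and 8.8.3:

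- Derive, for each patient and each post-baseline sample, a flag for ALT or AST >3 ULN with total bilirubin >2 ULN. State the timing rule, for example same sample date, because protocol 6.8.1 does not define the association in time. Say explicitly that unscheduled samples count, since SAP 8.11 leaves unscheduled data to listings unless data review selects them.
- Tabulate the number and percentage of flagged patients by cohort and overall, and list the cases with their values and dates.
- Reconcile the list with the reported SAEs. Send unreported cases to the site as queries for seriousness and causality assessment. Show any unresolved difference beside the reported SAE count rather than merging it in.
- Omit a baseline table. ALT or AST above 3 ULN is a non-inclusion criterion (protocol 4.2), so it would be empty for eligible patients. A plot of peak ALT against peak bilirubin is optional.

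SAP section 11 already records changes made after database lock. If lock has passed, do this as a documented additional analysis.

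The cost is one flag, one table, one listing and possibly a few late queries. No clinical criterion changes.

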### 6.3.1. Adverse events

The following AE categories will be studied:

- Treatment-emergent adverse events (TEAE)
- TEAE leading to treatment discontinuation (i.e. permanent or temporary)
- TEAE leading to permanent treatment discontinuation
- Mild/moderate TEAE (grade 1, grade 2, mild or moderate)
- Severe TEAE (grade 3, grade 4, grade 5 or severe)
- Drug-related TEAE
- Serious TEAE
- Serious TEAE leading to treatment discontinuation (i.e. permanent or temporary)
- Serious TEAE leading to permanent treatment discontinuation
- Serious drug-related TEAE

#### Definition of treatment-emergent AEs:

Treatment-emergent AEs are defined as any AE which occurs on or after the date of the first study-drug administration until the end of the follow-up visit (i.e. 18-month visit).

### 6.3.2. Laboratory examination

All laboratory parameters recorded in the CRF in sections “Hematology”, “Biochemistry” and “Urinalysis” will be used. For continuous data, the absolute change from baseline to each timepoints will be derived. In addition, continuous laboratory values will be compared to their reference ranges and classified as “<LLN”, “Normal” and “>ULN” at baseline and each timepoints.

For the following parameters, CTCAE grades will be derived as defined in Appendix 6 of the protocol:

- Hemoglobin
- Platelets
- Leukocytes
- Sodium
- Potassium
- Calcium
- Bicarbonates
- Chloride
- Glucose
- BUN
- Creatinine
- Alkaline phosphatase
- ALAT
- ASAT
- Total bilirubin
- Albumin
- Total protein

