1.4. Investigational Medicinal Product

Fexinidazole is a 2-substituted 5-nitroimidazole, orally active *in vitro* and *in vivo* against the two parasites *T.b. rhodesiense* and *T.b. gambiense*. The compound acts primarily as a biologically active prodrug, with the sulfoxyde and sulfone metabolites providing most of the trypanocidal activity. The efficacy of fexinidazole and of its metabolites in the treatment of HAT has been demonstrated in an extensive programme of preclinical and phase-I studies (179, 7).

Fexinidazole has received a positive opinion from the European Medicines Agency (EMA) and its use has been approved by the Democratic Republic of the Congo and Guinea.

To date, approximately 617 patients have received fexinidazole in the three studies, including 322 patients (52%) with late-stage HAT and 295 patients (48%) with early- or intermediate-stage HAT. Initial data on the safety of fexinidazole from the on-going studies in HAT indicate that the overall safety profile is satisfactory. No treatment interruptions have been reported. The most frequently observed adverse reactions in phase-I studies, which included a total of 154 healthy volunteers, primarily involved the central nervous system (headache) and gastrointestinal tract (nausea, vomiting, diarrhoea). In a phase-II/III study on fexinidazole for the treatment of Chagas disease, adverse reactions involving liver function, as well as cases of transient, reversible, asymptomatic neutropenia at grade 3 and 4, were reported (7).

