A study on fexinidazole concentrations in milk was conducted on lactating female albino rats after the administration of 800 mgeq/kg of [14C]-fexinidazole. Radioactive drug-related material was detected in milk at a concentration similar to that in plasma and in blood. Exposure to the radioactive drug-related material was approximately 80% of that measured in plasma, in terms of both C_{max} and AUC values.

On the basis of these findings, the same extent of exposure can be expected in breastfed human newborns. Median and maximum plasma exposure to M2, the main metabolite, observed in women participating in the FEX004 study were 529 and 930 μ g•h/mL respectively. This corresponds to a plasma M2 concentration of approximately 22 to 39 μ g/mL, from which it can be inferred that the concentration in breast milk will be from 18 to 31 μ g/mL. Thus, for newborns with a mean weight

Confidential Page 22 of 83

of 3 kg who consume around 500 mL of breast milk per day, this corresponds to total exposure to M2 in the range of 9.0 to 15.5 mg/day, i.e. 3.0 to 5.2 mg/kg.

Nevertheless, as a precautionary measure, pregnant women will be eligible to participate in the study only once they have reached the second trimester of pregnancy and will not be eligible for treatment on an out-patient basis.

The target population will also include patients whose health status is not as good as in earlier studies, within medically acceptable limits, as this is likely to be the case for some patients who will be treated in the future. Thus, the eligibility criteria for patients in the study are less strict that those in earlier studies on fexinidazole with, in particular, deletion of some criteria based on laboratory tests and on bodymass index (BMI).

As in early studies, in particular DNDiHATFEX006, children under 6 years of age will not be part of the target population for practical reasons related to the size of the tablets and difficulty in swallowing them.

Lastly, the study will provide additional laboratory data at 3 months and 6 months to supplement the existing laboratory safety database, with a particular focus on haematological and hepatic functions.

2. Study Objectives and Endpoints

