6.2.2. Baseline Assessment

Whether the patient is being considered for treatment in hospital or as an out-patient, the following procedures will be performed between Day -15 and Day -1 in order to stage the disease, to collect medical history and safety data, and to check the inclusion and non-inclusion criteria.

- Collection of informed consent / assent prior to administering any additional medication or to performing any non-routine assessment;
- Collection of CSF sample for WBC and disease staging;
- Karnofsky Performance Status,
- Review of inclusion and non-inclusion criteria
- Collection of demographic data;
- Collection of full medical history;
- Collection of signs and symptoms of HAT, in particular severity and time since the start of symptoms;
- Vital signs: body temperature, blood pressure, heart rate and respiratory rate;
- Diagnosis of malaria using RDT and/or thick blood smear and, if the result is positive, administration of antimalarial treatment;
- Treatment of helminthiasis, according to routine practices;
- Collection of concomitant medication;
- Physical and neurological examinations;

Confidential Page 34 of 83

- Laboratory safety assessments (see Appendix 3 Laboratory Tests; p 75) when possible, samples will be collected in the morning from patients in the fasting state;
 - Haemoglobin;
 - o Haematology: WBC, platelet count;
 - Biochemistry: albumin, alkaline phosphatase (ALP), alanine aminotransferase (ALT), aspartate aminotransferase (AST), blood urea nitrogen (BUN), chloride, creatinine, glucose, potassium, sodium, calcium, total bilirubin, bicarbonates and total protein;
 - Urine analysis (leucocytes, nitrites, pH, protein, glucose, ketone bodies, urobilinogen, bilirubin, blood and haemoglobin);
- Urine pregnancy test for women of child-bearing potential, to be done on Day -1;
- Triplicate digital ECG (CarTouch®), to be done on Day -1;
- Collection of SAEs.

6.3. IMP Dispensing: Day 0

If the patient is to be treated on an out-patient basis, the following procedures will be performed before s/he returns home to begin treatment.

- Check that all procedures for baseline assessment have been performed.
- Dispensing of IMP and, before returning home, reminder concerning instructions for taking the IMP and interview with Investigator to collect responses to questionnaire and ensure good understanding of the instructions by the patient and/or the caregiver;
- Collection of SAEs since signature of informed consent.

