Appendix 3 - Laboratory Tests

Laboratory Tests and Methods

All laboratory assessments will be described in a laboratory manual. Laboratory technicians have received specific training on these standard methods.

Biochemical tests

14 parameters will be analysed:

Albumin	Calcium
Alkaline phosphatase	Glucose
Alanine aminotransferase	Bicarbonates
Aspartate aminotransferase	Blood urea nitrogen
Total bilirubin	Sodium
Total protein	Chloride
Creatinine	Potassium

Haematological tests

- Haemoglobin assay
- White blood cells: count and differential count
- Platelets: count
- Microscope: full blood cell count (visual count) (see Investigator Manual)

Urine analysis

Urine dipsticks for laboratory safety analyses / Combur 9 Test®

White blood cells	Nitrites
рН	Glucose
Protein	Ketone bodies
Urobilinogen	Bilirubin
Blood	Haemoglobin

• Urine pregnancy test

CSF analysis (see Investigator Manual)

- Modified Single Centrifugation (MSC): detection of parasites
- Counting chamber: WBC count

Blood parasitology tests (see Investigator Manual)

- Thick/thin blood smears
- Woo test /CTC
- mAECT
- mAECT-BC

Confidential Page 75 of 83

Quantities of biological fluids required at each sampling timepoint

Screening Visit (Day -15 to Day -1)

	Type of test	Specific test	Number of samples	Quantity per sample (approx.)	Total quantity		
		Woo/CTC	1	100 μL			
	Parasitology	Thin/thick blood smear	1	≤ 300 µL	≤ 400 µL		
		mAECT (±BC)	1	5 mL	5 mL		
Blood		Haemoglobin	1	20 μL			
	Haematology	WBC	1	20 µL	170 µL		
	,	Platelet count	1	10 μL	(capillary blood ¹⁾		
		Differential WBC	1	20 µL	blood '		
	Biochemistry	14 parameters	1	100 µL			
Lymph	Parasitology	If lymph nodes detectable					
CSF	Parasitology	Modified Single Centrifugation	1	4 mL	4 mL		
Urine	Pregnancy		1	5 mL	10 ml		
Orine	Urine analysis	Combur 9 Test®	1	5 mL	10 mL		

End-of-Treatment Visit (Day 11)

	Type of test	Specific test	Number of samples	Quantity per sample (approx.)	Total quantity	
		Woo/CTC	1	100 μL		
	Parasitology	Thin/thick blood smear	1	≤ 300 µL	≤ 400 µL	
		mAECT (±BC)	1	5 mL	5 mL	
Blood	Haematology	Haemoglobin	1	20 µL		
		WBC	1	20 µL	170 µL	
		Platelet count	1	10 μL	(capillary	
		Differential WBC	1	20 µL	blood ¹⁾	
	Biochemistry	14 parameters	1	100 μL		
Lymph	Parasitology	If lymph nodes detectable				
Urine	Pregnancy		1	5 mL	40	
Offile	Urine analysis	Combur 9 Test®	1	5 mL	10 mL	

Confidential Page 76 of 83

Follow-up Visits at 3, 6, 12 and 18 months (per visit)

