Appendix 6 - CTCAE version 4.03 adapted

	CTCAE vs 0 SOC	CTCAE v4.0 Term	units	IIN	IIIN	Grade 1	Grade 2	Grade 3	Grade 4	Grade 5	CTCAE v4.0 AE Term Definition
Hematologie	01042 14.0000	OTOAL 14.0 Term	Units		UL.		Orace 2	Crade 5	Cinc. 4		OTONE PLONE TURN DEMINION
Hemoglobin	Blood and lymphatic system	Anemia - Man	g/dL	12.2	17.7	<12.2 - 10.0	<10.0 - 8.0	<8.0	Life-threatening consequences; urgent intervention indicated	Death	A disorder characterized by an reduction in the amount of hemoglobin in 100 ml of blood. Signs and symptoms of anemia may include pallor of the skin and mucous membranes, shortness of
	disorders Blood and lymphatic system	Anemia - Woman	g/dL	9.5	15.8	<9.5 - 8.5	<8.5 - 7.5	<7.5	Life-threatening consequences; urgent intervention indicated	Death	include pallor of the skin and mucous membranes, shortness of breath, palpitations of the heart, soft systolic murmurs, lethargy, and fatigability.
	disorders CTC criteria	Anemia	g/dL			<lln -="" 10.0="" dl<="" g="" td=""><10.0 - 8.0	<8.0 g/dL transfusion indicated	Life-threatening consequences; urgent intervention indicated	Death		</lln>	<10.0 - 8.0	<8.0 g/dL transfusion indicated	Life-threatening consequences; urgent intervention indicated	Death	
Platelets	Investigations	Platelet count decreased	nb/µL	126 000	438 000	<126,000 - 75,000	<75,000 - 50,000	<50,000 - 25,000	<25,000	-	A finding based on laboratory test results that indicate a decrease in
	CTC criteria	Platelet count	nb/µL			<lln -="" 75,000<="" td=""><75,000 - 50,000	<50,000 - 25,000	<25,000		number of platelets in a blood specimen.	</lln>	<75,000 - 50,000	<50,000 - 25,000	<25,000		number of platelets in a blood specimen.
		decreased									
Leucocytes	Blood and lymphatic system disorders	Leukocytosis	nb/µL	3100	9100	-	-	>100,000	Clinical manifestations of leucostasis; urgent intervention indicated	Death	A disorder characterized by laboratory test results that indicate an increased number of white blood cells in the blood.
	CTC criteria	Leukocytosis	nb/μL	_				>100,000	Clinical manifestations of leucostasis; urgent intervention indicated	Death	
	Investigations	White blood cell decreased	nb/µL	3100	9100	<3100-2500	<2500 - 2000	<2000 - 1000	<1000/mm3	-	A finding based on laboratory test results that indicate an decrease in number of white blood cells in a blood specimen.

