### **3.2 Laboratory examinations**

#### **3.2.1 Haematology:**

Statistical Table 3.2.1.1: Descriptive analysis of haematology parameters at baseline, at each time points and changes from baseline at each time points (mITT)

Statistical Figure 3.2.1.2: Changes over time of each haematology parameters (mITT)

Statistical Table 3.2.1.3: Shift tables between baseline and each time points of haematology parameters' severity (mITT)

Statistical Table 3.2.1.4: Shift tables of CTCAE grades between baseline and each time points of haematology parameters (mITT)

Statistical Figure 3.2.1.5: Scattergrams between baseline value and value at each time points of each haematology parameters (mITT)

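### Neutrophils get no derived CTCAE grade and no CTCAE shift table, although the protocol cites grade 3-4 neutropenia with this drug and plans differential counts

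*SAP*

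**What the plan says.** SAP 6.3.2 takes in all parameters from the CRF haematology, biochemistry and urinalysis sections for description. For a named list of 17 it adds that "CTCAE grades will be derived as defined in Appendix 6 of the protocol". The haematology entries in that list are haemoglobin, platelets and leukocytes. Appendix 6 of the protocol covers the same three. Its white-cell rows are leukocytosis and "White blood cell decreased", with reference limits of 3100 and 9100/µL. SAP 9.1 plans "Shift tables of CTCAE grades between baseline and each time points of haematology parameters" as Table 3.2.1.4.

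Protocol 1.4 reports that in a Chagas disease study of fexinidazole "cases of transient, reversible, asymptomatic neutropenia at grade 3 and 4, were reported", alongside liver reactions. Protocol 1.6 says that the extra 3- and 6-month laboratory data are collected "with a particular focus on haematological and hepatic functions".

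On collection, the protocol is not consistent. Appendix 3 lists "White blood cells: count and differential count" and shows a differential in the sampling tables for screening, Day 11, month 3 and month 6. The visit procedures in 6.2.2, 6.6 and 6.7.2 name haemoglobin and "Haematology: WBC, platelet count", with no differential.

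**The concern.** Neutropenia is the only haematological reaction that protocol 1.4 names, and it is named by grade. The planned graded output cannot show it. The liver reactions named in the same sentence are treated differently: the liver tests receive derived grades and, under SAP 8.8.3, categories by multiples of the upper limit of normal. Both are independent of anyone's clinical judgement.

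For neutrophils, a grade would arise only through the adverse-event route. SAP 6.3 analyses a laboratory abnormality as an AE only if the investigator reported it. Protocol 6.8.4 narrows this further after the observation period (Day 11 for out-patients, Day 13-18 for in-patients), when non-serious AEs are collected only if judged related to the drug. A transient, symptomless fall found at month 3 or 6 must therefore pass two judgements before it is graded. At stake is whether the report can set this cohort beside the Chagas study's neutropenia on the same scale.

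**Working it through.** The plan has no figure of its own on this point to reproduce. The check compares the lists and outputs, then asks whether leukocyte grading could do the same job.

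**Step 1: lists.** SAP 6.3.2 has 17 graded parameters, of which 0 are neutrophils. Appendix 6 has 0 neutrophil rows. Table 3.2.1.4 therefore has no neutrophil grades to tabulate.

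**Step 2: what the other outputs give, assuming neutrophils are in the CRF.**

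| Output (SAP) | Free of investigator judgement? | Counts patients by degree of neutropenia? |
|---|---|---|
| Descriptive statistics, change from baseline (8.8.3, Table 3.2.1.1) | Yes | No: summary values such as minimum and quartiles |
| Below, within or above reference range (6.3.2) | Yes | No: one class for every value below the lower limit |
| Time plots and scattergrams (Figures 3.2.1.2, 3.2.1.5) | Yes | No: lines and points, not counts by grade |
| Shift tables by clinical significance (8.8.3, Table 3.2.1.3) | No | No |
| Individual haematology listing (9.1, item 5.9) | Yes | No: the reader would have to grade each value |
| Listing of clinically significant abnormalities (8.8.3) | No | No |
| AE summaries (6.3, 8.8.2) | No | Only for reported events |
| CTCAE shift table (Table 3.2.1.4) | Yes | Yes for graded parameters; neutrophils are not among them |

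No row gives both properties for neutrophils.

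**Step 3: can leukocyte grading substitute?** Absolute neutrophil count = WBC × neutrophil share. In Appendix 6 a low white count is first graded below 3100/µL. A hypothetical patient with WBC 4000/µL and 10% neutrophils has 4000 × 0.10 = 400 neutrophils/µL. Because 4000 is above 3100, no grade is assigned.

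The documents give no neutrophil cut-offs, so I assume a range. At white count W, neutrophils fall below cut-off T once their share is under T/W:

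| Assumed T (/µL) | W = 3100 | W = 4000 | W = 9100 |
|---|---|---|---|
| 500 | 16.1% | 12.5% | 5.5% |
| 1000 | 32.3% | 25.0% | 11.0% |
| 1500 | 48.4% | 37.5% | 16.5% |

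All three white counts lie within the Appendix 6 reference limits and have no grade. The table shows that the gap can occur, not how often it would.

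**Step 4: what a graded count would allow.** If all 174 planned patients had gradable values and none reached grade 3, the upper limit of the two-sided 95% exact interval would be 1 − 0.025^(1/174) = 2.1%. The planned outputs do not supply the numerator for such a statement.

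**The case against.** The strongest reply is that neutrophils are not ignored. Every haematology parameter in the CRF is described, classed against its reference range, plotted, shift-tabled by clinical significance and listed patient by patient. A very low count would show in the minimum, the scattergram and the listing. A reader might infer from the missing grade that neutropenia would go unseen unless reported as an AE. The documents do not support that, and it is not the claim here.

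The AE route is also open to symptomless findings. Protocol 6.8.1 makes an abnormality reportable if it suggests organ toxicity and is new or abnormally worse since baseline. A reported neutropenia would be graded under CTCAE v4.03 (protocol 6.8.6) and count towards the grade 3 or higher endpoint. This stands, but it leaves grading to the investigator's decision to report.

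A reader might also take neutropenia as an established signal in HAT. Protocol 1.4 attributes it to a Chagas disease study, calls it reversible, gives no rate, and describes the overall safety profile in the HAT studies as satisfactory. It is a reason to look, not evidence of a problem in this population.

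Finally, the CRF is not among the documents and the visit procedures omit the differential, so availability of the data is not certain. That limits feasibility. It does not explain why a differential planned in Appendix 3 was left out of the grading list.

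**Conclusion.** The point holds as a gap in grading, not in analysis. The plan has no output that counts patients by neutropenia grade independently of investigator judgement, and leukocyte grades cannot replace it. The gap touches a descriptive secondary safety analysis; the primary endpoint and its confidence interval are unaffected. How many patients it would concern cannot be estimated from the documents. It is a cheap improvement worth making, on the assumption that the differential planned in Appendix 3 was recorded in the CRF.

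**What to change.** 1. Add absolute neutrophil count to the graded list in SAP 6.3.2, as recorded or derived as WBC × neutrophil percentage. Cite the CTCAE v4.03 neutrophil criteria directly, because Appendix 6 has no row to refer to.
2. Include it in Table 3.2.1.4. The template in SAP 9.2.11 shows grades 1 to 5 only, so add an ungraded category; otherwise a patient with a normal baseline has no cell.
3. List all derived grade 3 or higher neutrophil values, whether or not an AE was reported.
4. Label these as supplementary descriptive safety outputs, since SAP section 11 already records a change after database lock.
5. Reconcile the visit procedures in protocol 6.2.2, 6.6 and 6.7.2 with Appendix 3 on whether a differential is taken, and state how neutrophils are recorded in the CRF.

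The cost is one derived variable, one added table and one listing. If the differential was not captured, items 1 to 3 cannot be done and the report should say so.
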